4. Women of childbearing potential (based on medical history) must consent to use a medically accepted method of birth control (e.g., condoms and spermicide, oral contraceptive, Depo-Provera injection, contraceptive patch, tubal ligation) or abstain from sexual intercourse during the time they are in the study and using transdermal nicotine.
5. If current or past diagnosis of bipolar disorder, eligible if:
 - a. No psychotic features
 - b. MADRS: total score less than 8 (past 4 weeks), suicidal item score less than 1 (past 4 weeks)
 - c. Y-MRS: total score less than 8 (past 4 weeks), irritability, speech content, disruptive or aggressive behavior items score less than 3 (past 4 weeks)
 - d. No psychiatric hospitalization or Emergency Room visits for psychiatric issues in the past 6 months
 - e. No aggressive or violent acts or behavior in the past 6 months
6. Able to communicate fluently in English.
7. Capable of giving written informed consent, which includes compliance with the requirements and restrictions listed in the combined consent/HIPAA form.

4. Key Exclusion Criteria

Subjects who self-report and/or present with the following criteria will not be eligible to participate in the study.

Smoking Behavior:

1. Current enrollment in a smoking cessation program, or use of other smoking cessation medications in the last month or plans to do either in the next 2 months.
2. Daily use of chewing tobacco, snuff and/or snus, or electronic cigarettes.

Alcohol/Drugs:

1. Self-report current alcohol consumption that exceeds 25 standard drinks/week over the past 6 months. Subjects will be told to limit or avoid the use of alcohol while in the study to avoid any adverse reactions to the study medication.
2. Current untreated and unstable diagnosis of substance dependence (eligible if past use and if receiving treatment and stable for at least 30 days). Current untreated and unstable diagnosis of substance abuse requires Study Physician approval.
3. A positive urine drug screen for cocaine, amphetamines, methamphetamines, PCP, barbiturates and ecstasy (MDMA) at Intake, or any testing session (see Measures and Table 1 for details). Participants believed to have a false-positive result may continue in the study, with investigator approval.

Medical:

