 - b. Anti-psychotic medications as assessed on a case-by-case basis
 - c. Glucophage/metformin
 - d. Glyburide
 - e. Furosemide or digoxin
 - f. Nifedipine

- g. Cationic drugs (e.g., amiloride, digoxin, morphine, procainamide, quinidine, quinine, ranitidine, triamterene, trimethoprim, or vancomycin)
2. Participants who report taking prescription opiate-containing medications (Duragesic/fentanyl patches, Percocet, Oxycontin) will require physician approval prior to confirming final eligibility.
3. Current use of any smoking cessation medications (e.g., Chantix/varenicline, Zyban/bupropion, nicotine replacement therapy/gum/patch).
4. For safety reasons, HIV-infected smokers taking dolutegravir (Tivicay) or drugs that contain dolutegravir (e.g., Triumeq) should not take more than 1000 mg of metformin per day. Therefore, individuals taking dolutegravir will be forced randomized to either the placebo condition or the low dose condition.

Subjects will be instructed to refrain from using any study prohibited drugs/medications (both recreational and prescription) throughout their participation in the study. After final eligibility is confirmed, subjects who report taking contraindicated medication(s) over the course of the study period may only remain eligible if the Study Physician and/or Principal Investigator determines that the contraindicated medication(s) do/did not impact the study design, data quality, and/or subject safety/welfare. Subjects are permitted to take necessary prescription medications not included within the exclusion list during the study.

General Exclusion:

1. Current, anticipated, or pending enrollment in another research program over the next 2-3 months that could potentially affect subject safety and/or the study data/design as determined by the Principal Investigator and/or Study Physician.
2. Not planning to live in the area for the next two months.
3. Color blindness.
4. Any impairment (physical and/or neurological) including visual or other impairment preventing cognitive task performance.
5. Known allergy to study medication.
6. Planned radiologic studies involving the use of intravascular iodinated contrast materials (e.g., intravenous urogram, intravenous cholangiography, angiography, and computed tomography (CT) scans with intravascular contrast materials) during the course of study participation.
7. Inability to provide informed consent or complete any of the study tasks as determined by the Principal Investigator.

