This is a randomized, double-blind placebo-controlled, parallel arm pilot study of the effects of a low vs. high dose of metformin on abstinence-induced negative mood and cognitive deficits. Participants will complete Intake tasks to determine final eligibility before being enrolled into the study. Study visits will be completed either in-person at our center, or remotely (via phone or videoconferencing). Once eligibility is confirmed, subjects will attend a clinic visit (day 0) to establish baseline smoking rate, mood, and cognition. Subjects will then be randomized to one of three groups (low dose: 500 mg, high dose: 1500 mg, or placebo) and will complete 4 additional sessions (days 7, 14, 21, 23) to assess side effects, smoking rate, mood, craving, and withdrawal (Figure 1). Cognitive function will also be assessed on days 21 and 23. Subjects will be instructed to refrain from smoking for 24 hours prior to the laboratory session on day 23.

2. Study Visits

- **Telephone Screening.** Recruited subjects will complete an initial eligibility assessment in the HIV/AIDS clinic or over the telephone. This assessment reduces the likelihood that participants attend an Intake Session only to learn that they are ineligible or to allow us to ascertain physician's clearance should the participants have a medical condition that requires approval (e.g., mild hypertension). If a potential participant cannot be reached by phone, staff may send a text for the purposes of scheduling an initial eligibility screening phone call. This will help to reach potential participants who express interest in the study but do not answer phone calls from unrecognized numbers or do not regularly listen to voicemail messages. Texts will be sent from a central study account and not from the personal cellphones of any research staff. Participants who are initially eligible will be screened against our registration database to confirm that they are not currently participating in another research study at our Center and have not previously reported a condition or circumstance that would make them ineligible for the current study. Those participants who remain initially eligible will move forward with eligibility-determining tasks as part of the Intake session, which will be completed remotely and in-person. The Intake session must occur within 60 days of the initial eligibility screening or the participant will have to be re-screened.

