This session can be scheduled any time of day. However, the timing of this session will influence when the Day 21 and Day 23 testing appointments are scheduled. Ideally, the subsequent testing sessions would be at the same time of day but can be scheduled up to 3 hours earlier or later than the Baseline session. However, the sessions may go beyond 3 hours as determined by PI/Co-I discretion.

- Remote Check-In(Days 7 and 14). These sessions will be completed remotely via phone or videoconference and will last about 20 minutes. Participants will be asked to:

1. Report their smoking rate (timeline followback; TLFB)
2. Report their medication adherence
3. Report side effects and complete a concomitant medication review
4. Complete measures for mood, smoking urges, withdrawal symptoms, and subjective effects
5. Complete the MADRS, YMRS, Bipolar Disorder Additional Screener, if necessary
6. Review instructions for medication

This visit can be scheduled any time during the day and can be moved by plus or minus 1 day to accommodate for participant's schedule.

- Pre-Quit Testing Day (Day 21). Participants will be asked to bring their study medication to this visit. During this 2-hour visit, participants will complete the same activities they completed at the Baseline Session except that they will complete additional measures of pill count.

- Mandatory 24-H Abstinence Period. On Day 22, participants will receive a telephone call to remind them to begin their practice quit attempt approximately 24 hours before their scheduled 24-H testing session on Day 23. Participants will also be reminded that in order to remain eligible for the study, they must remain abstinent during this 24-hour period.

- 24-H Testing Day (Day 23). The 24-H Testing Day occurs after approximately 24 hours of abstinence from nicotine. The Testing Day Visit takes about 2 hours to complete and is split into two parts. The procedures participants will complete within each part of the Testing Day Visit are as follows:

- 24-H Testing Day Part 1

On Day 23 Part 1, participants will provide:

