1. A CO sample to verify abstinence. Mandatory abstinence will be biochemically confirmed by a CO reading of less than or equal to 8 ppm. If the CO reading is not less than 9 ppm, but there is a 50% reduction from the CO collected at the Baseline Visit, this will be considered sufficient and the participant may continue as scheduled. If neither condition is met, but participant reports abstinence, investigator approval will be needed for participant to continue with the session. If a participant smokes (self-reported or biochemically confirmed) during the mandatory abstinence period, they may be withdrawn from the study.
2. A urine sample for a urine drug screen and (if applicable) pregnancy test. If urine drug screen is positive, participants may be withdrawn from the study. Participants believed to have a false-positive result may continue in the study, with investigator approval.
3. Blood pressure (See Blood Pressure Procedures under Screening/covariate measures)
4. Have their blood glucose measured via a handheld glucose monitoring test (see Measures: Screening/Covariates). Subjects who have a low blood glucose level (i.e., less than 70 mg/dl) will be provided a beverage containing at least 15 g carbohydrates (e.g., 4 oz of fruit juice).
5. Report their medication adherence/review pill count*
6. Report side effects and concomitant medication review*
7. Complete questionnaires (mood, smoking urges, attention, and withdrawal symptoms) *

8. MADRS, YMRS, Bipolar Disorder Additional Screener, if necessary*
9. Complete a cognitive task battery (described below)

- 24-H Testing Day Part 2 (Programmed Lapse)

1. Participants will be instructed to smoke one of their own cigarettes in the CIRNA Smoking Laboratory.
2. Following the programmed lapse, participants will complete the assessments of the subjective and rewarding effects of the 'programmed lapse' cigarette (Table 1).

* Some tasks may be completed remotely to reduce the length of in-person visits.

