3.4 Secondary Outcomes

Smoking Rate (TLFB). We will assess the number of cigarettes smoked on each day throughout the study. A standard timeline follow-back (TLFB) method will be used [68], as we have done previously [69] to assess self-reported smoking rate.

Withdrawal Symptoms. The “Minnesota Nicotine Withdrawal Scale - Revised version”(MNWS_R) [70] captures the current state of nicotine withdrawal [71, 72]. The scale assesses eight DSM-IV items of nicotine withdrawal including: dysphoria or depressed mood, insomnia, irritability/frustration/anger, anxiety, decreased heart rate, difficulty concentrating, restlessness, and increased appetite/weight gain. Participants will rate the intensity of their symptoms on the following scale: 0 = none, 1 = slight, 2 = mild, 3 = moderate, 4 = severe and a summary score will be calculated. This will be administered at all study visits (except the Intake). Withdrawal will be assessed using a “past week” time reference for all visits except the 24-H testing visit on Day 23, which will use a 24-h time reference.

Craving. The 10-item brief QSU questionnaire on smoking urges [73] will be used to assess craving for cigarettes during the medication run-up period. The QSU-B contains 2 subscales (anticipation of reward, relief from negative affect). Craving has also been related to long-term cessation outcome in many, but not all, clinical studies [74]. This will be administered at all study visits (except the Intake). Similar to withdrawal symptoms, craving will be assessed using a “past week” time reference for all visits except the 24-H testing visit on Day 23, which will use a 24-h time reference.

Cigarette Ratings and Subjective Effects. The Cigarette Evaluation Scale (CES), developed to assess subjective effects of smoking [75], is an 11-item Likert-format measure. Questions include items for nausea and dizziness, craving relief, and

Table 1. Study Measures

State	Intake	Baseline	Remote Check-In ^b	Pre-Quit Testing	24-H Abstinent	Programmed Lapse
Study Visit Days	-1	0	7, 14	21	23 Part 1	23 Part 2
Screening Variables/Covariates						
Demographics	X					
Nicotine Dependence (FTND/Cigarette Brand)	X					
Smoking/ETOH History	X					
Medical History	X					
Height/Weight*	X	X		X		
Psychiatric/Substance Use Hx (MINI)	X					
Suicidal Ideation/Bx (C-SSRS)	X					
Bipolar Disorder Symptoms (MADRS, YMRS, additional screener) ^a	X	X	X	X	X	
Carbon Monoxide (CO)	X	X		X	X	X
Blood Pressure	X	X		X	X	

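### A participant who uses e-cigarettes or smokeless tobacco in the 24 hours before Day 23 can be confirmed as abstinent: the written instruction names only smoking, and CO is the only biochemical check

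*Combined protocol and SAP*

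**What the plan says.** **Entry.** Key Exclusion Criteria, Smoking Behavior, item 2 excludes "Daily use of chewing tobacco, snuff and/or snus, or electronic cigarettes". Less-than-daily use of these products is not an exclusion. The Medication exclusions add "Current use of any smoking cessation medications (e.g., Chantix/varenicline, Zyban/bupropion, nicotine replacement therapy/gum/patch", which covers nicotine replacement but neither e-cigarettes nor smokeless tobacco.

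**Instruction.** Study Procedures, 1. Procedures states: "Subjects will be instructed to refrain from smoking for 24 hours prior to the laboratory session on day 23". The Protocol Abstract and Study Design, 2. Design say the same. Under Mandatory 24-H Abstinence Period, the Day 22 call reminds participants that "in order to remain eligible for the study, they must remain abstinent during this 24-hour period". It does not say abstinent from what.

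**Intended state.** Study Visits, 24-H Testing Day (Day 23): "The 24-H Testing Day occurs after approximately 24 hours of abstinence from nicotine".

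**Verification.** 24-H Testing Day Part 1, item 1: "Mandatory abstinence will be biochemically confirmed by a CO reading of less than or equal to 8 ppm". If that is not met, "but there is a 50% reduction from the CO collected at the Baseline Visit, this will be considered sufficient". If neither holds but the participant reports abstinence, an investigator must approve continuation. Smoking in the period, whether self-reported or shown biochemically, may lead to withdrawal from the study.

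**Records.** On the timeline follow-back (TLFB), section 3.4 says: "We will assess the number of cigarettes smoked on each day throughout the study". The Urine Drug Screen paragraph in section 3.1 lists drugs of abuse, with no nicotine or cotinine. The Concomitant Medication Review (section 3.2, also done on Day 23) covers medications and substances that may alter the response to study drug, and does not name nicotine products.

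**The concern.** The title and rationale concern withdrawal from nicotine. The Background section gives the mechanism: in mice, chronic nicotine raises AMPK phosphorylation, withdrawal reverses this, and metformin is meant to restore it. On that hypothesis, someone still taking nicotine has not entered the state that metformin is supposed to correct.

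The Day 23 session supplies the abstinent measurement for both primary outcomes. If some participants counted as abstinent are still taking nicotine, the measured effect of abstinence is pulled toward zero. So is any metformin-placebo contrast that depends on it. The pilot's stated purpose is to provide effect sizes for later research, and a bias of this kind would pass into that planning unseen. Table 1 lists no measure of other nicotine products on Day 21 or Day 23, so the size of the problem could not be established afterwards either.

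**Working it through.** **1. Following the rules through for one participant.** The plan has no figure to reproduce on this point, so the check is mainly textual. Take a smoker who vapes or uses snus on some days.

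| Step | Rule | Result |
|---|---|---|
| Entry | Daily use excludes | Eligible |
| 24-hour instruction | Refrain from smoking | Met if no cigarette is smoked |
| Day 22 call | Remain abstinent, no product named | Ambiguous |
| CO test | 8 ppm or less, or a 50% fall from Baseline | Can be passed without smoking |
| Self-report | Smoking in the period | Nothing to report |
| Urine panel | Drugs of abuse | No nicotine marker |
| TLFB | Cigarettes per day | Not recorded |
| Concomitant review | Medications and certain substances | Product not named; answer not tied to abstinence status |

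The CO row relies on one piece of general knowledge that the documents do not state: exhaled CO reflects combustion, so vaped or oral nicotine does not raise it. No row reliably identifies the nicotine use.

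**2. Size if use is equal across arms.** Let *f* be the share of completers who use such a product in the window and *r* the share of withdrawal it relieves. The measured abstinence effect is the true effect × (1 − *f r*). The documents give neither *f* nor *r*; the values below are assumptions, with *r* = 1 as the upper end.

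- *f* = 5%: factor 0.95
- *f* = 10%: factor 0.90
- *f* = 20%: factor 0.80

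With equal use, the arm difference shrinks by the same factor. Take illustrative true abstinence effects of 1.0 on placebo and 0.7 on metformin, a difference of 0.30. The measured difference is 0.30 × 0.95 = 0.285, 0.30 × 0.90 = 0.27, or 0.30 × 0.80 = 0.24. With *r* = 0.5 and *f* = 10% the factor is 1 − 0.05 = 0.95, so the loss halves to 5%.

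**3. Size if use differs by arm** (same effects, *r* = 1).

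- Placebo 5%, metformin 2.5%: 0.95 − 0.7 × 0.975 = 0.95 − 0.6825 = 0.2675, a loss of 11%.
- Placebo 20%, metformin 10%: 0.80 − 0.63 = 0.17, a loss of 43%.
- Placebo 10%, metformin 20%: 0.90 − 0.56 = 0.34, a gain of 13%.

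Both the direction and the size depend on the assumed imbalance.

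**4. Against the pilot's precision.** The plan's 18 per group gives a 95% half-width for a mean of t(0.975, 17)/√18 = 0.497 SD, which agrees with its claim of less than half an SD. For a difference between two such groups it is about ±0.68 SD. If one unit above is taken as one SD (an assumption), every shift shown is at most 0.13 and lies well inside that interval.

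**The case against.** The best reply is that the construct is mostly smoking abstinence. The primary outcome under Objectives is defined after 24 hours without smoking, and CO with a no-smoking instruction suits that definition. The description of Day 23 as abstinence from nicotine appears once. This has force: part of the problem is a mismatch of wording. But the title, the mechanism and that sentence all point to nicotine, and the rules do not secure it.

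A reader might infer that participants are told only not to smoke and are checked only by CO. The documents do not support that. The Day 22 call asks them to remain abstinent during a practice quit attempt, and self-reported smoking counts alongside CO. The reminder script and case report forms are also not in the documents. What can be said is that the protocol names no other product.

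A reader might also take the 43% loss in the unequal case as the likely damage. It rests on assumed two-fold unequal use, 20% use on placebo in a single 24-hour window, and full relief. Daily users are excluded, and no figure in the documents supports such a rate.

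Finally, a reader might infer that cigarettes per day would be wrong if participants switched to vaping in the run-up. It would not be: that outcome is smoking behaviour, and the fall in cigarettes would be real.

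It is also true that the pilot makes no formal tests and that its sampling error exceeds any shift shown. That limits the urgency. It does not remove the bias, which a larger later trial planned on these estimates would inherit.

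**Conclusion.** The gap stands. With the written rules followed exactly, a less-than-daily e-cigarette or smokeless-tobacco user who takes nicotine in the 24 hours can be confirmed as abstinent, which conflicts with the protocol's own description of Day 23. The textual finding is firm, subject to the general fact that CO marks combustion. The size is not known. Under equal use of 5% to 20% and full relief, the abstinence effect and the arm difference shrink by 5% to 20%. Partial relief would make the loss smaller, and unequal use could move it either way. The correction is worth making because it is cheap and because the trial, as written, could not show later whether the problem occurred.

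**What to change.** 1. In Study Design, 2. Design, in Study Procedures, 1. Procedures, and in the Mandatory 24-H Abstinence Period text (including the Day 22 reminder), instruct participants to refrain from all nicotine and tobacco products for the 24 hours, naming e-cigarettes, smokeless tobacco and nicotine replacement. Align the Protocol Abstract.
2. In 24-H Testing Day Part 1, item 1, add a question on any such use since the start of the period, record the answer, and do not label reported users as confirmed abstinent.
3. Keep reported users in the data and give the primary summaries with and without them. Withdrawing them after randomisation could itself distort the comparison if use is related to arm or to severity of withdrawal.
4. Optionally, record non-cigarette nicotine use alongside the TLFB, as an aid to interpreting changes in smoking rate.

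The cost is a change of wording, one Day 23 item and, if wanted, one extra TLFB column, with no new assay, visit or staff. There are two limits. The question relies on self-report, and the $50 bonus for completing all visits gives some reason to conceal use, so hidden use stays undetected. A few more participants will be flagged as not abstinent.

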2.1 Post-Study Follow-up

If necessary, subjects may be contacted after study participation to clarify self-report data collected during their active study participation. Although procedures are in place to ensure data accuracy during active participation, there are instances when it may be necessary to conduct a post-study follow-up to maintain data accuracy when analyzing study outcomes. If study staff are unable to contact a subject for follow-up, no further action will be taken.

3. Description of Measures and Variables

3.1 Screening/Covariate Measures

Demographics and Smoking History. Standard questionnaires will be administered remotely or in-person at Intake to collect the following data: demographics (age, gender, marital status, education), age at smoking initiation, cigarette brand, length of prior abstinence periods and current smoking rate. The Fagerstrom Test for Nicotine Dependence (FTND) will also be administered. The FTND is a 6-item, self-report measure of nicotine dependence derived from the Fagerstrom Tolerance Questionnaire [53]. The FTND scale has satisfactory internal consistency (Cronbach's alpha=. 64) and high test-retest reliability ($r=. 88$) [54].

Medical History. A medical history (self-report) and a physical examination will be conducted remotely or in-person at Intake to review for any contraindications listed previously. If the NP/provider is off-site, staff will coordinate a telehealth visit for the participant while they are at the center, via phone, FaceTime or BlueJeans (both HIPAA-compliant). The medical history (including height and weight) will be completed by a research staff member. For the HIV-infected group, duration since HIV/AIDS diagnosis, mode of transmission, and viral load and CD4+ counts will be assessed. Current medication usage will be tracked at each time-point.

Psychiatric/Substance Use History. Current major depression, lifetime prevalence of psychosis, bipolar disorder, schizophrenia, hypomanic/manic episodes, and substance abuse will be determined via self-report during the phone screen and via semi-structured interview using the Mini International Neuropsychiatric Interview (MINI). The MINI is a 10-15-minute structured interview developed by the World Health Organization to assess major DSM-IV Axis 1 psychiatric diagnoses. This instrument permits both current (past 30 days) and lifetime assessments of psychiatric illness, and recent data support its reliability and validity [55]. The MINI will be administered by a trained research staff member remotely or in-person as part of the Intake session. There will be 100% review of paper MINIs by the PM, a licensed clinical social worker, with relevant training, to maintain quality control. [name], a clinical psychologist, will serve as back-up when needed.

Suicidal Behavior and Ideation (C-SSRS). All participants will complete the C-SSRS (Screening Version) with a trained staff member remotely or in-person. The C-SSRS is a structured interview that assesses the suicidal behavior and suicidal ideation in subjects [56, 57]. Occurrence of lifetime suicidal behavior is defined as having answered "yes" to at least 1 of the 4 suicidal behavior sub-categories (actual attempt, interrupted attempt, aborted attempt, and preparatory acts or behavior). Current suicidal ideation is defined as having answered "yes" to at least 1 of the suicidal ideation sub-categories (wish to be dead, non-specific active suicidal thoughts, active suicidal ideation with any methods without intent to act, active suicidal ideation with some intent to act [without specific plan], and active suicidal ideation with specific plan and intent) over the past month.

Carbon Monoxide. Carbon monoxide (CO) measures will be made using a Vitalograph Breath CO Analyzer (McNeil International, Inc., Lenexa, KS). The manufacturer will have calibrated this device within the past year. A new, disposable cardboard mouthpiece will be provided for each participant. The device has a digital screen which reports CO levels in parts per million (ppm). Participants will be asked to provide a CO breath sample by taking a large breath, holding their breath for two seconds, releasing the breath, then taking another deep breath and holding their breath for 10 seconds, as per the recommendations of the American Thoracic Society. Then, when instructed to do so, participants will exhale as forcefully and as long as they are comfortably capable. The largest value displayed is recorded during all CO breath samples. CO breath samples will be collected at each in-person study visit.

Blood Pressure. At the Intake, participants presenting with elevated blood pressure (i.e., systolic blood pressure greater than 159 and/or diastolic blood pressure greater than 99) will have a second blood pressure reading taken after a ten-minute period in which the participants will be instructed to sit comfortably. If, after the second reading, systolic blood pressure remains greater than 159 and/or diastolic remains greater than 99, the participant will be ineligible for the study, unless determined otherwise by the Study PI/Co-I or Study Physician, upon review.

Blood pressure will be measured at all subsequent in-person visits. If participants present with elevated blood pressure (i.e., systolic blood pressure greater than 159 and/or diastolic blood pressure greater than 99) at any subsequent visit, the staff will follow the same steps listed above. If, after the second reading, systolic blood pressure remains greater than 159 and/or diastolic remains greater than 99, the Study Physician or Study PI will be consulted to discuss whether the participant should continue taking the study medication. Research staff will follow up with the participant accordingly.

Shipley Institute of Living Scale. All participants will complete the Shipley Institute of Living Scale (SILS) remotely or in-person as part of the Intake session. The SILS is a self-administered test designed to assess general intellectual functioning in adults and adolescents and to aid in identifying cognitive impairments [58]. The scale consists of two subtests, a 40-item vocabulary test and a 20-item test of abstract thinking. The total administration time is 20 minutes (10 minutes per subtest). A trained member of the study staff will score the test. The SILS correlates with the Wechsler Adult Intelligence Scale-Revised (WAIS-R) Estimated IQ Test and is considered a highly reliable assessment tool; with a good total score internal consistency (Cronbach's alpha= .92).

Urine Drug Screen. The urine drug screen will be administered at Intake and each testing session (baseline, day 21, and day 23). The urine drug screen requires about 30ml of urine and indicates whether the subject has recently taken any exclusionary drugs (cocaine, PCP, amphetamines, methamphetamines, ecstasy and barbiturates). Participants with a positive urine drug screen for any substance listed above other than THC, opiates, or methadone will be deemed ineligible. The rationale for excluding these participants is because one of the primary outcomes in this study is cognitive function. Thus, excluding individuals who screen positive for substances that may interfere with their ability to perform the cognitive tasks (e.g., benzodiazepines may slow reaction times) reduces this potential source of variability. In an effort to remain CLIA-compliant, results from urine drug screening will not be shared with participants. Participants will be informed that the testing is for research purposes only and that they will be informed of their eligibility status, but not of the specific testing results. In addition, the current protocol does not utilize PennChart and therefore, results of the screening will not be added to participants' electronic medical records.

Urine Pregnancy Test. At the Intake and each testing session (Baseline, day 21, and day 23), participants will be supplied with a simple, CLIA-waived urine pregnancy screen and informed that pregnant women are not advised to participate in this research study. Participants will then be instructed to administer the pregnancy test independently and will inform study staff if they would like to continue participation after they have administered the pregnancy screen. Participants will be informed that there is no penalty for discontinuing participation at this point in the visit and that they will still receive travel reimbursement for the visit.

Depression and Anxiety. The Hospital Depression and Anxiety Scale (HADS) [59], a 14-item self-report measure, will assess depression and anxiety symptoms. This scale correlates with clinical ratings of depression and anxiety [59] and is used with HIV-infected individuals [60]. Because depressive symptoms are associated with deficits in cognitive function [61] and lower HAART adherence [62], the HADS will be evaluated as a potential moderator of abstinence effects on cognitive function and relapse. The HADS will be administered at each visit.

Bipolar Disorder Symptoms: If a diagnosis of bipolar disorder is self-reported or revealed via the MINI at Intake, the Montgomery-Asberg Depression Rating Scale (MADRS), Young Mania Rating Scale (YMRS), and a Bipolar Disorder Additional Screener will be completed, remotely or in-person, at all study sessions to evaluate and monitor the presence and severity of bipolar disorder symptoms.

Functional Impairment. The Patient's Assessment of Own Functioning Inventory (PAOFI) will be used to assess cognitive difficulties in everyday life. The PAOFI assesses areas such as mental acuity, employment, social functioning, shopping, cooking, housekeeping, laundry, driving, use of public transportation, maintaining schedules, medication management, financial management, understanding media events, and child care [63]. The degree of functional impairment is used to distinguish between categories of HANDs [64]. This measure will be used to evaluate whether those with baseline functional impairment, or functional impairment during nicotine withdrawal, have more difficulty maintaining abstinence.

Risk Assessment Battery (RAB). This is a self-report questionnaire designed to assess high-risk behaviors associated with HIV transmission. The measure yields two scores: Drug Risk Behavior (e.g. sharing needles, IV drug use) and Sex Risk Behavior (e.g., exchanging sex for drugs, unprotected sexual activity).

The BASIS-24. The BASIS-24 is a 24 item self-report inventory designed to measure mental health status from the patient's point of view. The items cover 6 domains including: depression/functioning, interpersonal relationships, psychotic symptoms, alcohol/drug use, and emotional lability.

The SF-12. This measure is used to assess health-related psychosocial functioning. This well-validated, self-report tool measures 8 health-related dimensions: physical functioning, bodily pain, role limitations due to physical health problems, role limitations due to personal or emotional problems, general mental health, social functioning, energy/fatigue, and general health perceptions.

Quick Inventory of Depressive Symptomatology- Self Report (QIDS). The QIDS is a 16-item self-report measure designed to assess the severity of depressive symptoms using the criterion symptoms designated by the DSM-IV.

Liver Function, Gamma-glutamyl Transpeptidase, and Creatinine tests. One 8.5ml blood sample will be drawn at the Intake visit. Blood will be collected and placed in a serum-separator tube (SST) and mixed thoroughly. Samples will be centrifuged at 3100 rpm for 10 minutes. If separation is not complete, the sample will be centrifuged at the same RPM for an additional 5 minutes. The following chemistry will be assessed:

1. Total protein.
2. Albumin.
3. Globulin.
4. Albumin/Globulin ratio.
5. Bilirubin (total, conjugated and unconjugated)
6. Aspartate amino transferase (AST).
7. Alanine amino transferase (ALT).
8. Alkaline phosphatase (AP).
9. Gamma glutamyl transferase (Gamma-GT)
10. Creatinine.

Neuroinflammation. Blood samples will be collected at Baseline and Pre-Quit Testing visits to explore the association of biomarkers of neuroinflammation using a 6 cytokine assay (e.g., C-Reactive Protein; Interleukin-6) with smoking status and cognition (HIV+ group only). Whole blood will be collected in two EDTA tubes and two SST tubes at each visit and delivered to the Laboratory Biomarkers, Quantitative Pharmacology, Neuroimaging, and Neurobehavioral Characterization Core at the Penn Mental Health AIDS Research Center for storage and analysis.

Blood Glucose. Because metformin may lower blood glucose, glucose levels will be measured at each in-person study visit. As recommended by the National Institute of Diabetes and Digestive and Kidney Diseases (NIDDK), blood glucose levels in non-diabetic individuals less than 70 mg/dl may indicate hypoglycemia. The Abbott Precision Xtra Blood Glucose & Ketone Monitoring System will be used to measure blood glucose (https://freestyleserver.com/Payloads/IFU/2017july/ART24315-002_rev-A_WEB.pdf). This device is indicated for home

and professional use. As recommended by the manufacturer, the device will be cleaned and disinfected after each use. A trained member of the research staff will obtain a drop of blood (approximately 0.3 microliter) via a finger prick using a lancing device. The device provides a blood glucose reading within 60 seconds. Individuals who have a blood glucose level less than 70 mg/dl will be provided a beverage containing 15 g of carbohydrate (e.g., fruit juice or soft drink) and asked to wait in the laboratory. After 15 minutes, blood glucose will be rechecked to ensure it is greater than 70 mg/dl before allowing the participant to leave. Participants who present with blood glucose less than 70 mg/dl may be withdrawn from the study.

